5.1.2. Definitions

5.1.2.1. Description of Study Days

Study day for an event will be calculated from the first dose of study drug as (date of event – first dose date + 1) if the date of event is on or after the first dose date, or (date of event – first dose date) if the date of event is before the first dose date. That is, Study Day 1 is the first day of treatment with study drug rFVIII Fc. Study Day -1 is the day immediately preceding Study Day 1. There is no Study Day 0 in this study. Study days will be included in the data listings where indicated on the listing shells. "NA" for "not applicable" will be used to indicate that a patient did not receive the respective study drug.

5.1.2.2. Visit Windows

Screening Visit

Screening assessments must be completed within a total of 8 weeks from the start of screening activities (with the exception of informed consent, which may have occurred earlier). If more than 8 weeks have elapsed, and the patient is not enrolled in the study, then the Nijmegen inhibitor and FVIII antibody assessments must be repeated. Other screening assessments that are not completed must be completed within an additional 8 weeks, except for the collection of the genotyping sample. If necessary, a genotyping sample could be sent to the central laboratory at a subsequent interim visit.

Baseline Incremental Recovery Visit

Baseline IR Visit activities are performed as soon as practicable once all eligibility criteria were met and the patient is enrolled. This visit may be conducted along with other baseline

assessments on the same day as screening, once the patient has been enrolled, or as part of a separate baseline IR visit, as long as the patient has not yet had more than 3 doses of rFVIII Fc. Samples for IR calculations are taken when the patient is in a non-bleeding state. Baseline IR requires a washout from rFVIII Fc of at least 24 hours prior to the predose sample collection.

Treatment Period Visits

Patients on episodic or prophylactic treatment in this study participate in regular interim visits for follow up, as well as follow up at specific ED milestones. Regular interim visits were every 12 (± 2) weeks.

ED Milestone Visits

Unscheduled visits are performed at the following ED milestones to perform protocol-mandated inhibitor tests: 5 ED (± 1 ED), 10 ED (10-15 ED), 20 ED (20-25 ED) and 50 ED (50-55 ED).

ITI Visits

After a patient on episodic or prophylactic treatment is confirmed as having high- or low-titer inhibitors with poorly controlled bleeding, the patient participates in ITI visits. Pre-ITI assessment is on ITI Day 0. The first interim ITI visit is ITI Week 2 (± 3 days). Subsequent ITI interim visits are every 4 weeks until a negative titer is confirmed. After a negative titer is confirmed, interim visits are every 4 weeks until ITI Complete Success or a maximum of 33 months of treatment (see Section 7.4.9).

Patients with a confirmed negative inhibitor titer and confirmed IR $\geq 66\%$ of expected who have not yet achieved the criteria for ITI complete success, will undergo PK evaluation for $t_{1/2}$ every 12 weeks.

Post Immune Tolerance Success Visits

Patients who fulfill the criteria for ITI complete success or 33 months of ITI treatment then transition to a “tapering” regimen over a minimum period of 12 weeks with the aim of starting a prophylactic rFVIII Fc regimen, and are monitored for relapse for up to 9 months.

Tapering visits are every 4 weeks (± 1 week) within a 12-week period.

Follow-up monitoring for relapse visits are every 12 weeks (± 2 weeks) within a 9 month period.

Surgery Visits

Surgery visits are as follows:

- Pre-Surgery Visit (Week -4 to Week -2). Not required for emergent surgery.
- Preoperative Assessment (Day of Surgery). If surgery is delayed by ≥ 8 weeks, preoperative assessments are to be repeated. These include assessments of FVIII activity and Nijmegen-modified Bethesda assay. For minor surgery, the Investigator will be in contact with the patient’s parent/caregiver to determine when the patient may return to the regular prophylactic treatment regimen.
- Postoperative Visit (1 to 2 weeks after surgery). Visit is required for major surgeries only.

- Last Postoperative Visit. This visit occurs when the Investigator determines that the patient can return to the regular prophylactic treatment regimen. This visit is not required if the return to the regular prophylactic treatment regimen occurs at the Postoperative Visit. If the patient is withdrawn from the study, then the patient completes the ET/EOT Visit assessments at least 2 weeks after surgery.

End-of-Treatment Visit

End of Treatment (EOT) for individual patients is defined as follows:

- Any individual patient who completes at least 50 EDs of rFVIIIIFc and is not on an ITI regimen has completed treatment.
- A patient undergoing ITI with rFVIIIIFc has completed treatment if either of the following occurs:
 - The patient achieves complete ITI success and completes the tapering and monitoring periods.
 - The patient completes 33 months on an ITI regimen without achieving complete ITI success (that is, ITI failure or partial ITI success).
- Individual patients may also be required to end treatment because one of the following has occurred:
 - The patient meets the criteria for early withdrawal.
 - Study stopping rules are met.
 - EOS is reached.

Final Safety Follow-Up Visit

The Final Safety Follow-Up Visit (by telephone or in person) will be conducted within 7 to 14 days after the last dose of rFVIIIIFc to assess the patient's status, collect AEs and/or SAEs and concomitant medications and procedures and follow up on open AEs and SAEs.

5.1.2.3. Baseline

Unless specified otherwise, for the purpose of analyses involving change from baseline during treatment with rFVIIIIFc, baseline is defined as the last non-missing measurement (that can be used for data analysis i.e. was not taken during a surgical/rehabilitation period) taken prior to the first dose of study medication rFVIIIIFc.

If a patient requires rescreening during the study, then baseline characteristics for the summary table will be taken from the first screening visit.

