### 4.2.2.3. Schedule of Activities: Immune Tolerance Induction

The following schedule applies to subjects who are eligible for ITI, as described in Section 10.2.5.2. The specific follow up tests to be performed following ITI depend on the outcome of ongoing testing as described in Section 10.2.7.4 and Figure 2.

Activities	Pre-ITI Assessment (ITI Day 0)	Week 2 Visit (at 2 wks ±3 days)	ITI Visits		
			Every 4 Weeks (±2 Weeks)	Every 4 Weeks (±2 Weeks)	Every 4 Weeks (±2 Weeks)
			Starting at ITI Week 4, Until negative titer is confirmed	Starting at time of confirmed negative titer, Until IR ≥66% of expected is confirmed	Starting at time of IR confirmed ≥66 % Until ITI Complete Success a OR 33 Months of treatment
Informed Consent b	X				
Physical Examination	X	X	X	X	X
Weight (kg)	X	X	X	X	X
Vital Signs c	X	X	X	X	X
Hematology d,e	X		X	X	X
Blood Chemistry e,f	X		X	X	X
rFVIII Fc Dosing g	X	X	X	X	X
Nijmegen-Modified Bethesda Assay (Inhibitor Assay) h	X	X	X	X	X
Blood Sample for Exploratory Biomarker Characterization i	X		X	X	X
FVIII Activity for Incremental Recovery j			X	X	X
Half-life Evaluation (Factor VIII activity only to be done every 12 weeks once IR ≥66% confirmed) k					X l
Anti-rFVIII Fc Antibody	X	X	X	X	X
EPD Review, including rFVIII Fc Dosing Accountability m	X	X	X	X	X
Injection Site Inspection n	X	X	X	X	X
Adverse Events	<<<ONGOING; Monitor and record at all visits; telephone call every month>>>				

CONFIDENTIAL

The information contained herein may not be used, disclosed, or published without the written consent of Bioverativ Therapeutics Inc.

Serious Adverse Events	<<<ONGOING; Monitor and record at all visits; telephone call every month>>>
Concomitant Therapy/Procedures Recording o	<<<ONGOING; Monitor and record at all visits; telephone call every month>>>

AE = adverse event; DHA=Directions for Handling and Administration; EOT = end of treatment; ET = early termination; FVIII = coagulation factor VIII; ITI = immune tolerance induction; rFVIII Fc = recombinant coagulation factor VIII Fc fusion protein; SAE = serious adverse event.

- a See Section 10.2.7.4.2 for criteria for complete success.
- b Informed consent must be obtained prior to the ITI assessments beginning at Week 0.

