9.4.1.1. Change from Baseline

Hematology and chemistry results at baseline and post baseline visits, along with change from baseline, will be summarized with descriptive statistics by visit and for the end of study. Data from unscheduled visits will be excluded from this analysis. In the event of retests or repeat assessments at the same time point, the last non-missing evaluable measurement will be used for the purpose of analysis.

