9.4.1.3. Potentially Clinically Significant Laboratory Abnormalities

Abnormal laboratory values will also be evaluated by determining the number and percentage of patients with at least one potentially clinically significant laboratory abnormality over the course of the study that also represents a worsening from baseline. The potentially clinically significant

levels are based on Grade 2 or higher thresholds from the Common Toxicity Criteria for Adverse Events (CTCAE v 4.02 2009) where possible, or were defined by Bioverativ’s Pharmacovigilance group.

Patients who have a post baseline laboratory value that meets the criteria for being potentially clinically significant but do not have a baseline value will be included in the numerator for determining the percentage of patients with an abnormality. Percentages will be based on the number of patients with at least one post baseline value for the given laboratory test. Threshold levels for potentially clinically significant laboratory abnormalities are provided in [Table 2](#) (hematology) and [Table 3](#) (chemistry). Data collected from unscheduled visits will be included in this analysis.

Table 2: Threshold Levels for Potentially Clinically Significant Hematology Abnormalities

	Low	High
Neutrophils	$<1.5 \times 10^9/L$	NA
Eosinophils	NA	$>1.6 \times 10^9/L$
Hemoglobin	$<100 \text{ g/L}$	Increase in $>20 \text{ g/L}$ above ULN
Hematocrit	$<30\%$	$\geq 60\%$
Platelet count	$\leq 75 \times 10^9/L$	$\geq 700 \times 10^9/L$

NA = not applicable

Table 3: Threshold Levels for Potentially Clinically Significant Chemistry Abnormalities

	Low	High
Liver		
ALT/SGPT	NA	$>3 \times \text{ULN}$
AST/SGOT	NA	$>3 \times \text{ULN}$
Total bilirubin	NA	$>1.5 \times \text{ULN}$
GGT	NA	$>2.5 \times \text{ULN}$
Renal		
Creatinine	NA	$>1.5 \times \text{ULN}$
Electrolytes		
Chloride	$\leq 90 \text{ mmol/L}$	$\geq 118 \text{ mmol/L}$
Other		
Glucose	$<3.1 \text{ mmol/L}$	$>8.9 \text{ mmol/L}$
Total protein	$\leq 45 \text{ g/L}$	$\geq 100 \text{ g/L}$

NA = not applicable, ULN = upper limit of normal

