Summary of physician's global assessment of the response for ITI regimens
Summary of health outcomes for episodic and prophylactic regimens
Summary of incremental recovery (IR) (IU/dL per IU/kg) for episodic and prophylactic regimens
ITI

	Statistical Analysis Plan	Final v1.0
---	----------------------------------	-------------------

Summary of ITI response and relapse
Surgery
Investigators'/surgeons' assessment of patients' hemostatic response to rFVIIIFc post surgery
Number of injections and dose required to maintain hemostasis during major surgery
Estimated total blood loss during major surgery
Total rFVIIIFc consumption (IU/kg) per major surgery
Summary of number of bleeds after surgery per major surgery
Adverse events
Overall summary of rFVIIIFc treatment-emergent adverse events by treatment regimen
Overall summary of rFVIIIFc treatment-emergent adverse events by inhibitor subgroup
Overall summary of rFVIIIFc treatment-emergent adverse events by inhibitor sub-classification
Overall summary of rFVIIIFc treatment-emergent adverse events by treatment regimen and EPD entry compliance
Summary of rFVIIIFc treatment-emergent adverse events by treatment regimen
Summary of rFVIIIFc treatment-emergent adverse events by inhibitor subgroup
Summary of rFVIIIFc treatment-emergent adverse events by inhibitor sub-classification
Summary of rFVIIIFc treatment-emergent adverse events by treatment regimen and EPD entry compliance
Summary of rFVIIIFc treatment-emergent adverse events by treatment regimen and preferred term in descending order of incidence
Summary of rFVIIIFc treatment-emergent serious adverse events by treatment regimen
Summary of rFVIIIFc treatment-emergent adverse events by severity and treatment regimen
Summary of rFVIIIFc treatment-emergent adverse events by relationship to treatment and treatment regimen
Summary of severe rFVIIIFc treatment-emergent adverse events by treatment regimen and preferred term in descending order of incidence
Summary of rFVIIIFc treatment-emergent adverse events leading to treatment discontinuation or withdrawal by treatment regimen
Routine laboratory
Summary of laboratory results and change from baseline for episodic and prophylactic regimens: Hematology
Summary of laboratory results and change from baseline for ITI regimen: Hematology
Shifts from baseline to minimum/maximum post-baseline value for laboratory results: Hematology

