Summary of shifts from baseline to minimum/maximum post-baseline value for laboratory results: Hematology
Summary of potentially clinically significant laboratory abnormalities: Hematology
Summary of laboratory results and change from baseline for episodic and prophylactic regimens: Blood Chemistry
Summary of laboratory results and change from baseline for ITI regimen: Blood Chemistry
Shifts from baseline to minimum/maximum post-baseline value for laboratory results: Blood Chemistry

	Statistical Analysis Plan	Final v1.0
---	----------------------------------	-------------------

Summary of shifts from baseline to minimum/maximum post-baseline value for laboratory results: Blood Chemistry
Summary of potentially clinically significant laboratory abnormalities: Blood Chemistry
Inhibitors
Summary of inhibitor development by Nijmegen-modified Bethesda assay
Summary of peak titer inhibitor development by Nijmegen-modified Bethesda assay
Summary of time to inhibitor development
Other Safety
Summary of anti-rFVIII Fc antibodies
Summary of vital sign results and change from baseline for episodic and prophylactic regimens
Summary of vital sign results and change from baseline for ITI regimen

List of listings

Background/demography
Listing of lot numbers for study drug
Listing of protocol versions consented to
Listing of end of study disposition
Listing of demographic and baseline characteristics
Listing of caregiver’s demography
Listing of medical and surgical history
Listing of informed consent date and analysis populations
Listing of hemophilia history – diagnosis and diagnostic factors
Listing of Hemophilia history – bleeding history 3 months prior to screening
Listing of hemophilia history – pre-study FVIII treatment
Listing of risk factors
Listing of prior and concomitant medication taken through the end of study visit
Listing of concomitant medication taken after the end of study visit and prior to follow-up
Listing of maternal concomitant medication taken through the end of study visit
Listing of maternal concomitant medication taken after the end of study visit and prior to follow-up
Listing of other therapy or concomitant procedures
Listing of major and minor protocol deviations
Exposure/dosing
Listing of all injections and treated bleeding episodes
Listing of injections to treat a bleed
Listing of exposure
Listing of dose and consumption endpoints
Listing of prescribed dose and regimen changes
Listing of compliance endpoints
Efficacy

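### The three ITI change-from-baseline tables measure from before the first rFVIIIFc dose, so the change they show includes whatever arose before ITI began

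*SAP*

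**What the plan says.** SAP 5.1.2.3 sets a single default baseline "for the purpose of analyses involving change from baseline during treatment with" rFVIIIFc. It is the last non-missing usable value "taken prior to the first dose of study medication" rFVIIIFc, unless another rule is given. ITI is itself treatment with rFVIIIFc, so the default covers it.

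SAP section 12 lists three ITI outputs that depend on a baseline:

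- "Summary of laboratory results and change from baseline for ITI regimen: Hematology"
- "Summary of laboratory results and change from baseline for ITI regimen: Blood Chemistry"
- "Summary of vital sign results and change from baseline for ITI regimen"

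The laboratory method in SAP 9.4.1.1 reads "Hematology and chemistry results at baseline and post baseline visits, along with change from baseline, will be summarized with descriptive statistics by visit" and names no regimen-specific reference. SAP 9.5 treats vital signs the same way and counts height and weight among them.

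The ITI schedule in Protocol 4.2.2.3 opens with a column headed "Pre-ITI Assessment (ITI Day 0". Weight, vital signs, hematology and blood chemistry are marked there. Height is not marked at Day 0 or at any other ITI visit.

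**The concern.** A table titled as change for the ITI regimen will be read as change on ITI. SAP 5.1.1.1 limits the post-baseline data to time on the regimen, but the reference value stays at study entry. Everything between the two is carried into the ITI column: main-study treatment, development of the inhibitor, bleeding while the inhibitor was present, and the child's growth. A hemoglobin fall from bleeding before ITI, or weight gained before ITI, would appear as change under ITI.

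Elsewhere the documents keep these phases apart. Protocol 16.5.2.2 summarizes adverse events during ITI separately, and SAP 5.4.7 splits safety data at the inhibitor date. The three change tables are out of line with that separation. The protocol's primary objective is safety, so a reader will want to know what changed after ITI began.

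**Working it through.** **Step 1: is the default overridden?** I looked for an ITI baseline in the sections where one could stand.

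- SAP 5.1.1.1 restricts the data to time on the regimen. It does not move the reference.
- SAP 5.1.2.2 names the Day 0 visit but does not use it as a baseline.
- SAP 5.4.8 defines the start of the ITI period and attaches no baseline.
- SAP 7.4.9 uses the subject's Baseline IR for ITI response. That is a different purpose.
- SAP 9.4.1.1, 9.5 and 10 contain nothing specific to ITI.

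The default therefore applies to all three tables.

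**Step 2: what the tables show.** Let B be the study baseline, D the ITI Day 0 value and Y(t) the value t days into ITI. Then

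Y(t) − B = (D − B) + (Y(t) − D).

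The first bracket arose before ITI. With D as the reference it is zero by construction.

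**Step 3: length of the pre-ITI gap.** The plan states no figure to reproduce, so this is an illustration. Inputs:

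- Prophylactic interval of 3 to 5 days (Protocol 10.2.3).
- Confirmatory sample about 2 to 4 weeks, or 14 to 28 days, after the first positive sample (Protocol 10.2.5.1.2).
- Assumed: regular prophylaxis from the first dose, the ED at onset, and Day 0 at the time of confirmation.

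The lag from first dose to Day 0 is L = (ED − 1) × interval + confirmation time.

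- Onset at ED 10: 9 × 3 + 14 = 41 days, to 9 × 5 + 28 = 73 days.
- Onset at ED 20: 19 × 3 + 14 = 71 days, to 19 × 5 + 28 = 123 days.

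**Step 4: share of the displayed change that predates ITI.** If a measure drifts linearly, the share is L / (L + t). The lower and upper ends for ED 10 to 20 are:

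- Week 4: 41 / (41 + 28) = 59%, to 123 / (123 + 28) = 81%.
- Week 12: 41 / (41 + 84) = 33%, to 123 / (123 + 84) = 59%.
- 33 months: t = 33/12 × 365.25 = 1,004 days, giving 41 / 1,045 = 4%, to 123 / 1,127 = 11%.

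Over a wider range of onset:

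| Onset (ED) | Lag L (days) | ITI Week 4 | ITI Week 12 | 33 months |
|---|---|---|---|---|
| 5 | 26–48 | 48–63% | 24–36% | 3–5% |
| 10 | 41–73 | 59–72% | 33–46% | 4–7% |
| 20 | 71–123 | 72–81% | 46–59% | 7–11% |
| 50 | 161–273 | 85–91% | 66–76% | 14–21% |

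A preceding episodic phase (Protocol 10.2.2) or a deferred ITI start (Protocol 10.2.7) lengthens the gap. Earlier onset or closely spaced doses for bleeds shorten it.

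**The case against.** The best defense is that the default is a legitimate choice. ITI uses the same drug, the pre-treatment value is the only drug-naive one, and change from it is a valid cumulative safety summary. That stands. It is a reason to keep that column, not a reason to omit change from ITI start in tables titled for the ITI regimen.

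There is also some mitigation. Observed values are tabulated alongside change, and all laboratory values and vital signs are listed (SAP 9.4, 9.4.1.1, 9.5), so a reader could partly reconstruct the ITI change. The table shells and programming specifications mentioned in SAP 5.3.1 and 5.3.2 are not available here. If they define an ITI baseline, the SAP should say so.

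The illustration gives time gaps and shares under linear drift. It does not estimate bias for any laboratory test or vital sign, and the hemoglobin example is hypothetical.

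Three stronger readings are tempting, but the documents do not support them.

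- *This distorts the highest-exposure phase.* ITI has the highest regular dose, but Protocol 7.2.1 expects exposure to be much lower during ITI because of the inhibitor.
- *The shift and potentially clinically significant tables need the same change.* Their titles in SAP section 12 name no regimen. SAP 9.4.1.3 asks about abnormalities over the whole study, using a value "that also represents a worsening from baseline". The pre-rFVIIIFc reference suits that question, and re-anchoring could drop abnormalities that arose on rFVIIIFc before ITI.
- *A worsening from an abnormal Day 0 value would be hidden if the screening value was similar.* If the two values are similar, both baselines give the same change.

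**Conclusion.** The point holds for the three tables of change from baseline for the ITI regimen, and only for those. Under the SAP as written, they report change since before the first rFVIIIFc dose, not change since ITI start.

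The distortion is concentrated at early ITI visits and fades over a long course of ITI. The sizes above rest on linear drift, prophylaxis every 3 to 5 days from the first dose, onset at ED 10 to 20 for the main range, and no delay between confirmation and ITI start.

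A reader might infer that the primary result is at risk. It is not: inhibitor incidence (SAP 9.4.3) does not use this baseline, and neither do the adverse event summaries. A reader might also infer that a Day 0 baseline would take growth out of the ITI tables. It would remove only growth before ITI. Growth during up to 33 months of ITI in young children remains, with no comparator to separate it. Height adds nothing to the case, because it has no Day 0 value.

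This is a modest defect in descriptive secondary safety summaries. It is worth correcting because the correction is cheap.

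**What to change.** Add to SAP 5.1.2.3, in words such as: *For the three summaries of change from baseline for the ITI regimen (hematology, blood chemistry, vital signs), baseline is the last non-missing value before the first ITI dose, normally the Pre-ITI (ITI Day 0) assessment. Change from the pre-rFVIIIFc baseline is shown in a second column.*

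Three details:

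- Anchor on the first ITI dose, not on the Day 0 label. Dosing is also marked at that visit, and post-dose vital signs should not serve as baseline.
- Leave height out of the change from ITI baseline.
- Leave unchanged the study-wide shift and potentially clinically significant tables, and the Baseline IR reference for ITI response.

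The cost is one SAP sentence, a baseline flag in programming and an extra column in three tables. No new data are needed.
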